Participants are considered enrolled in the study when they have completed informed consent. Randomization occurs immediately after the baseline appointment.

Informed Consent Process

Details of the study are reviewed with the prospective study participant by a research assistant who is trained and cleared to conduct assessments and is knowledgeable about the research study. This discussion is a critical component of the consent process and the prospective study participant will be given adequate time for this discussion and to read the written consent form. The research assistant is available to answer questions about the study including participant responsibilities, benefits, risks, and alternatives. The participant reviews the consent form and it is signed and dated by both the participant and study staff member conducting the assessment. A copy of the signed consent form will be given to the participant and the original will be kept securely by the project coordinator separate from other assessment materials.

Post-COVID: Participants review written consent information prior to their baseline appointment. The baseline survey link directs participants to a landing page containing detailed consent information. At the beginning of the baseline assessment, study staff provides an oral review of consent information and confirms age eligibility via Zoom. After reviewing this information, participants are asked to affirm their consent/assent to participate. A copy of the electronic consent form is emailed to the participant upon request.

Randomization Process/Systems

Participants are randomized at the end of their baseline assessment into one of two intervention conditions: 1) delivery of the 4 session PARTNER intervention or 2)

delivery of 4 education sessions. Each participant's condition is tracked in the access tracking database maintained by the project manager.

The study employs a stratified block randomization procedure with equate study conditions based upon 1) age discrepancy between partners, 2) relationship length, and 3) race and ethnicity using Qualtrics.

Schedule of Assessments

Sessions occurs approximately once per week for three weeks beginning one week after completion of the baseline assessment and session 1. There is a 12 week window for intervention completion, i.e. all four sessions must be completed within 12 weeks of the baseline assessment.

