Participants complete the first follow-up assessment 3 months after the baseline, and subsequent follow ups at 6, and 9 months after baseline with a final appointment scheduled for 12 months following the baseline appointment. Study staff should aim to schedule and complete these follow-ups as close as possible to each target date. To keep track of longitudinal data collection dates, assessment visit windows will be defined as 15 days prior and after the target as "in window." The assessment visit window for the 12 month follow-up ends 30 days after the target date. Site study staff should prioritize the completion of sessions before the first follow-up assessment, and should not schedule this follow-up less than 12 weeks after baseline if a participant is available to complete any additional sessions first.

Post-COVID: The 12-month assessment window ends 60 days after the target date.

Component	Baseline	Session 1	Session 2	Session 3	Session 4	3-Month Follow-Up	6-Month Follow-Up	9-Month Follow-Up	12-Month Follow-Up
Informed Consent	Х								Х
Randomization	Х								
CASI	Х					Х	Х	Х	Х
TLFB	Х					Х	Х	Х	Х
HIV Testing (Rapid for those not on PrEP –	Х						Х		Х

Architect for those on PrEP)								
STI Testing	Х					Х		Х
Fingernail Assay for Drugs	Х				Х	Х	х	Х
Dried Blood Spot (For those on PrEP)	х				Х	Х	Х	Х
PrEP Video			X					
Video Recall Survey for those who seen the Video				Х	х			х
Session feedback				Х				
Qualitative Interview								х

Managing and Tracking Study Visits

There are two different types of visits during the study timeline:

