Drug use. During TLFB interviews, participants indicated whether they used any of 10 different drug types. Responses produced two count variables indicating the number of days participants used cannabis and the number of days they reported the use of any illicit drugs, including: cocaine, crack, methamphetamine, ecstasy, ketamine, GHB, and psychedelics. Self-reported drug use was corroborated by fingernail assay. See supplemental material for details.

Current PrEP uptake was assessed using a single survey item, "Have you ever been prescribed PrEP (HIV pre-exposure prophylaxis)?" Participants taking PrEP reported days they missed their PrEP on the TLFB interview. Responses were used to create a dichotomous variable indicating whether or not participants took PrEP on at least 57% of days (corresponding to at least 4 days out of 7 on average). Self-reported PrEP adherence was corroborated with DBS results. See supplemental material for details.

Sexual HIV TRB. During TLFB interviews, participants indicated days they had (insertive or receptive) anal sex with any casual partners and whether a condom was used. Responses were aggregated to create a variable indicating the number of times the participant had CAS with a casual partner. If participants were prescribed PrEP and reported missing 13 doses or fewer, they were assigned a value of 0, reflecting that the use of PrEP on at least 4 of 7 days is sufficient to achieve reductions in HIV TRB (28). Self-reported CAS with casual partners was corroborated by bacterial STI diagnosis. See supplemental material for details.

Putative moderators

Relationship satisfaction was assessed using the approximation to ideal subscale of Kurdek's (29, 30) Multiple Determinants of Relationship Commitment Inventory (MDRCI). The subscale consists of 4 items (e.g., "My current relationship comes close to matching what I would consider to be my ideal relationship"). Response options ranged from 1 (strongly disagree) to 5 (strongly agree). Total score reliability was good (Cronbach's $\alpha = .848$).

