Several considerations led to the inclusion of model covariates. Consistent with guidance for the analysis of data from randomized controlled trials that utilize stratified randomization (16), stratification variables were included as covariates in regressions predicting latent growth factors. The COVID-19 pandemic and recovery corresponded with changes in substance use and sexual behavior among SMM. To account for this, models incorporated a dichotomous, timevarying predictor indicating whether an assessment occurred before or after March 2020. All models were calculated using full-information maximum likelihood estimation in Mplus Version 8.0. This permitted the retention of all randomized cases consistent with the intent-to-treat paradigm. Model significance was evaluated using a robust log-likelihood $\chi 2$ test comparing the log-likelihood of the specified model to a null-model – in which all structural coefficients associated with the regression of latent growth factors on condition and site were constrained to be zero. Where model results were significant, the effect of the PARTNER intervention was evaluated by examination of regression parameters for Slopes 1 and 2. Given the directional nature of hypotheses, single-sided p-values were used to determine the

significance of the intervention effect. When evaluating the significance of putative moderators and associated interaction terms, two-sided p-values were used.

Power analyses

We utilized the *Test for the Ratio of Two Negative Binomial Rates* module in PASS 19 to evaluate power to detect between-condition differences in drug use frequency at any one follow-up time point. Power (1-beta) was set to .80 and the probability of type II error (alpha) was set to .05. The number of exposures was set to 30 (the number of days of use assessed in the TLFB). The rate of use in the education condition was set to 3, 6, and 9. Meanwhile dispersion values of 1, 2, and 4 were tested. Power was highest at low levels of dispersion and high based rates of use in the education condition. Under these circumstances, the study has power=.80 to detect a rate ratio of 0.70 or a 30% reduction in drug use instances. At high levels of dispersion and low base rates, the study would be expected to detect a rate ratio of 0.48.

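### The TRB rule caps PrEP doses missed but sets no minimum for doses taken, so casual-partner CAS before a man's first dose can be scored as 0

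*Combined protocol and SAP*

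**What the plan says.** All of the outcome definitions are in the Primary outcomes part of the MEASURES section.

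- **TRB count.** Casual-partner CAS from the TLFB interview is summed to one figure per assessment: "Responses were aggregated to create a variable indicating the number of times the participant had CAS with a casual partner".
- **Zeroing rule.** "If participants were prescribed PrEP and reported missing 13 doses or fewer, they were assigned a value of 0", with the justification "reflecting that the use of PrEP on at least 4 of 7 days is sufficient to achieve reductions in HIV TRB".
- **PrEP data.** "Participants taking PrEP reported days they missed their PrEP on the TLFB interview". No start date or count of doses taken is described. The survey item on PrEP asks whether it was ever prescribed.
- **Companion adherence variable.** This one is defined on days taken: "whether or not participants took PrEP on at least 57% of days (corresponding to at least 4 days out of 7 on average".
- **Window length.** The Power analyses section gives 30 days for drug use ("the number of days of use assessed in the TLFB"). No window is stated for TRB.
- **Hypotheses and test.** The Quantitative Analysis Plan expects more PrEP initiation and adherence under PARTNER and, in consequence, less TRB. The Detailed analytic plan uses one-sided p-values for the intervention effect.

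**The concern.** A cap on missed doses stands in for a minimum of doses taken only when the number of days on PrEP is fixed. For a man who starts during the window it is not fixed. His whole-window count can be set to 0 although part of his CAS, possibly most of it, happened before he took any PrEP. That is CAS without PrEP, which is how the Power analyses section describes this outcome.

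Starting PrEP is one of the behaviours PARTNER aims to produce. If it does so, more men in that arm start within an assessment window and more pre-dose CAS is deleted there. The error then runs in the direction of the one-sided hypothesis on a primary outcome. At baseline, randomisation should balance it between the arms; at follow-up, nothing does.

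**Working it through.** **Where 13 comes from.** Four of 7 days taken means 3 of 7 missed. Over 30 days, 30 × 3/7 = 12.86, which rounds to 13. So the cut-off reproduces by rounding, and it presupposes 30 days on PrEP. Strictly, 13 missed leaves 17/30 = 56.7%, just under the companion variable's 57%; 18/30 = 60% is the first value that meets it.

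**Set-up.** Let a man start on day s of a 30-day window and take every dose from then on. Doses taken = 31 − s. Days before the first dose = s − 1. The plan does not say whether those earlier days count as missed, so both readings are worked.

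**Literal reading (a dose not yet prescribed cannot be missed).**
- Missed = 0 for every s, so every starter is set to 0.
- A start on day 25 gives 6 doses, 6/30 = 20% of days. With CAS spread evenly, 24/30 = 80% of it came before the first dose. At the planning rates of 1, 3 and 5 events, 0.8, 2.4 and 4.0 events are erased.
- From day 18 on, at most 31 − 18 = 13 doses can be missed. Such a man scores 0 even if he takes none.

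**Alternative reading (pre-start days count as missed).**
- Missed = s − 1, so the man is set to 0 only if s ≤ 14.
- Starts on days 15 to 30 keep their count. Starts on days 2 to 14 still lose 1 to 13 pre-dose days, up to 13/30 = 43% of the window.

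**Average over start days.** Assume start days are uniform on 1 to 30, adherence is full after the start, and CAS is even over the window and equal in starters and other men. The mean share of a starter's CAS that is pre-dose and erased is:
- literal: (0 + 1 + … + 29)/(30 × 30) = 435/900 = 48.3%
- alternative: (0 + 1 + … + 13)/(30 × 30) = 91/900 = 10.1%

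**Effect on an arm's mean.** If a share q of the arm starts in the window, the mean falls by q times that share:

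| q (assumed) | Literal | Alternative |
|---|---|---|
| 5% | 2.4% | 0.5% |
| 10% | 4.8% | 1.0% |

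The documents give no value for q. The percentages are of the arm's CAS before any zeroing. Relative to the smaller count left after men with full cover are rightly set to 0, the same loss is proportionally larger.

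**What a doses-taken rule would do.** With full adherence after the start, at least 17 doses is met only by starts up to day 14, and at least 57% of 30 days only by starts up to day 13. Later starters would keep their count. Pre-dose CAS of men starting from day 2 up to that day would still be erased unless it is counted separately.

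**The case against.** **The late-starter case depends on an unstated reading.** The cut-off of 13 makes sense only over a fixed 30 days, and the companion variable, built from the same interview, is a share of days taken. Both suggest that pre-start days may have been treated as not taken, and late starters would then not be zeroed. This stands as a limit: it cuts the illustrated error about fivefold. It does not remove it, because pre-dose CAS is still erased for starts on days 2 to 14.

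**A reader might infer that about half of any TRB reduction would be an artefact.** The documents do not support that. The figure arises if in-window starters are the only difference between arms, since evenly spread starts leave about half the window before the first dose. The Power analyses section considers about 51% v 35% on PrEP. Take those shares, all assumed adherent, with 10% v 2% of men starting in the window and half of each starter's CAS pre-dose. The literal rule then gives 0.49/0.65 = 0.754; counting pre-dose CAS gives 0.54/0.66 = 0.818. The artefact is (0.818 − 0.754)/(1 − 0.754) = 26% of the apparent reduction. With 16% v 5% the second ratio is 0.57/0.675 = 0.844 and the share is 37%. None of these start shares comes from the documents, and 16% in one window would equal the whole planned difference (51 − 35).

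**A reader might also infer that new starts cluster just before the 3-month visit.** It is true that "all four sessions must be completed within 12 weeks of the baseline assessment" and that "Participants complete the first follow-up assessment 3 months after the baseline". But 12 weeks is the outer limit. Sessions are planned about weekly, which puts session 3, with the PrEP video, at roughly weeks 2 to 3. A 30-day window before a 3-month visit opens around day 91 − 30 = 61, about week 9. A man who starts promptly is on PrEP for the whole window, and one who continues is covered at later visits too. The direction of the error needs only more in-window starts under PARTNER, not clustering.

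**Conclusion.** The point holds. As written, the rule does not implement its own 4-of-7 justification for men who start PrEP within the window, and no other section corrects it. A primary outcome is misclassified on either reading of a missed dose, and the plan's silence on which reading applies means the variable cannot be reproduced from the text.

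The direction favours PARTNER if PARTNER raises PrEP starts. The size is unknown and probably modest, because only men starting within the window before a given assessment are affected. The worked figures rest on an inferred 30-day window, uniform start days, full adherence after the start and evenly spread CAS. They do not show that the TRB result would be reversed or that a particular share of it is spurious.

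**What to change.** 1. Base the zeroing rule on days PrEP was taken over all window days, using the plan's own 57% (4 of 7) criterion as in the companion adherence variable. Score days before the start or after stopping as not taken. State the TRB window, and whether 17 of 30 days meets the criterion.
2. Count CAS that occurred before the first dose where the start date is recorded or can be derived. The plan describes CAS days and missed-PrEP days but no start dates. Where the date is missing, state the assumption made and vary it.
3. Report unadjusted casual-partner CAS as a sensitivity analysis. It answers a different question, because it ignores PrEP cover, but it is free of this error.

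The cost is the re-derivation of one variable and a few sentences in the SAP, and possibly a slightly smaller TRB effect. The Measures section is written in the past tense, so if the outcome has already been analysed, both derivations should be shown side by side.

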- 2- Participants NOT on PrEP, will be administered a rapid HIV Test named "Determine Ab/Ag" which detects HIV antibodies and antigen P24 (the last one is a very sensitive part of this specific test and can detect early acute HIV infections).

At baseline we test for Urethral and Rectal Gonorrhea & Chlamydia presence. The testing method for Urethral G&C will involve the participant urinating in a sterile urine collection cup then to pipette just a portion of that urine sample into a sample tube in order to be sent for testing to Sunrise medical Laboratory. For Rectal detection we will provide the participant with an anal swab collection kit, and send the specimen for STI detection to Sunrise Medical Laboratory.

We will collect participant's fingernails and potentially toenails in case the sample is not enough, to test illicit drug use in the last 6 months, this 5-Panel drug assay will be conducted by USDTL Laboratory.

A second vial of blood will also be collected at the same time as the HIV test vial with participants reporting being on PrEP, to perform dried blood spot (DBS) cards to test for PrEP adherence, which will be sent to Colorado Antiviral Pharmacology Laboratory.

Post-COVID Specimen Collection

HIV and STI tests are completed using tests shipped and processed by Molecular Testing Labs (MTL). Prior to the RA administered portion of the baseline assessment and 6- and 12-month follow-ups, participants are mailed a package containing an athome OraQuick testing kit for HIV, self-administered rectal and urethral gonorrhea and chlamydia testing kits, one dried blood spot (DBS) card (if on PrEP), collection

materials (alcohol prep pads, lancets, gauze pad, and adhesive bandages), an instruction card, and a postage-paid shipping envelope. During the RA administered portion of the baseline, 6M, and 12M, the RA will review instructions and demonstrate the collection procedure. The RA will then remain on the Zoom call to provide any additional guidance as needed during the collection procedure. Participants will then place the collected specimens in the addressed envelope for shipping to the lab for processing. Participants will also be mailed a fingernail collection kit to examine drug use rates during all assessments.

Incentives and Compensation

Participants will be compensated up to \$380 for full participation in the study. They will receive:

\$50 for completing a Baseline assessment.

\$20 for each completed session (up to \$80 total).

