Communication skills. Self-disclosure, social anxiety, assertiveness, and empathy subscales of the Interpersonal Communication Competence Scale (31) assessed aspects of communication skills. Each subscale was assessed by 3 statements (e.g., "I can put myself in others' shoes" and "It's difficult to find the right words to express myself"). Participants evaluated each statement using a 5-point scale Likert-type scale ranging from 0 ("Almost never") to 4 ("Almost always"). Total score reliability was good (Cronbach's $\alpha = .787$).

Quantitative Analysis Plan

The primary hypotheses are that SMM receiving the PARTNER intervention will be more likely to initiate and/or be adherent to PrEP throughout the follow up period. As a result, it is hypothesized they will have a lower probability of TRB. In addition, it is hypothesized that the PARTNER intervention will be associated with lower levels of drug use (number of use instances) compared to the education condition.

Corroboration of self-reported behavior with biomarkers

Self-reported drug use was corroborated by fingernail assays. At baseline and all follow-ups, at least 80% of participants who tested positive for cannabis indicated at least one instance of cannabis use. In addition, at least 60% of those who did not test positive for cannabis on fingernail assays indicated they used cannabis at least once. At baseline, and all follow-ups, at least 55% of those who tested nail positive for cocaine, crack, or amphetamine use reported at least one instance of illicit drug use. In addition, 12% of those who did not test positive for illicit drug use on nail samples self-reported the use of at least one drug.

Self-reported PrEP adherence was corroborated with DBS results. At baseline and all follow-up time points, no fewer than 69% of participants who reported taking their PrEP on 57% of days or more had a DBS test result of 700 units of TFV-DP per DBS punch or greater at all follow-up time points. One participant at baseline and another at the 3month follow-up reported missing more than 57% of their PrEP but produced a DBS result of 700 units of TFV-DP per DBS punch or more.

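### The fingernail results do not corroborate self-reported cannabis use and only partly support self-reported illicit drug use, and no between-arm analysis uses them

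*Combined protocol and SAP*

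**What the plan says.** Under Primary outcomes, the drug-use entry defines two counts from the timeline follow-back (TLFB) interview: days of cannabis use and days of any illicit drug use. It then states "Self-reported drug use was corroborated by fingernail assay" and refers to supplemental material. The section on corroboration with biomarkers repeats the statement ("Self-reported drug use was corroborated by fingernail assays") and gives four figures:

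- Cannabis, nail positive: "at least 80% of participants who tested positive for cannabis indicated at least one instance of cannabis use".
- Cannabis, not nail positive: "at least 60% of those who did not test positive for cannabis on fingernail assays indicated they used cannabis at least once".
- Illicit drugs, nail positive: "at least 55% of those who tested nail positive for cocaine, crack, or amphetamine use reported at least one instance of illicit drug use".
- Illicit drugs, not nail positive: "12% of those who did not test positive for illicit drug use on nail samples self-reported the use of at least one drug".

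The document gives no counts, agreement statistic, criterion for agreement or results by arm.

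The two measures cover different periods. Specimen Collection Pre-COVID says nails are taken "to test illicit drug use in the last 6 months, this 5-Panel drug assay will be conducted by USDTL Laboratory". Power analyses gives the interview period: "The number of exposures was set to 30 (the number of days of use assessed in the TLFB".

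They also cover different drugs. The illicit-use outcome includes ecstasy, ketamine, GHB and psychedelics, while the nail-positive group is defined by cocaine, crack or amphetamine.

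The Detailed analytic plan models the self-reported counts and tests the intervention effect with one-sided p-values. It describes no nail-based outcome or sensitivity analysis. Equivalency Checks does use biological markers of substance use, but only for baseline comparisons.

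**The concern.** Calling a self-report corroborated tells the reader that an objective measure bears it out. That matters here because drug use is a primary outcome reported in an interview by men who know which sessions they attended; no masking of participants is described. PARTNER elicits change talk about drug use and builds personal change plans. Education is delivered by lecture, discussion and video. If willingness to report use shifted differently in the two arms, a one-sided test of self-reported days could not separate less use from less reporting. Agreement pooled over arms would not settle this even if it were good. The nail samples are the only objective drug measure in the trial, and the plan does not compare them between arms.

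**Working it through.** **Inputs.** The four percentages come from the corroboration section. They are observed figures without numerators or denominators, so they cannot be reproduced. Three are lower bounds. The 12% is given without a visit. I read the cannabis bounds as holding at baseline and every follow-up, and I read *did not test positive* as a negative result. The text does not say whether men without a usable sample are in that group.

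**1. Cannabis.** At the stated bounds:

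- Difference: 80 − 60 = 20 points.
- Ratio: 0.80/0.60 = 1.33.
- Odds ratio: (0.80/0.20)/(0.60/0.40) = 2.67.

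Because both values are lower bounds, 1.33 is not itself a limit. The ratio can lie anywhere from 0.80/1.00 = 0.80 to 1.00/0.60 = 1.67. For an assumed nail-positive prevalence of 10% to 60%, kappa at the stated bounds is about 0.06 to 0.21.

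The difference in window does not explain this. Use in the past 30 days lies inside a 6-month window, so a man who truthfully reports recent use should fall within the assay's reach. At least 60% of men who were not positive nevertheless reported use.

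**2. Illicit drugs.** At the stated figures:

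- Nail positive with no reported use: at most 100 − 55 = 45%, at the worst visit.
- Difference: 55 − 12 = 43 points.
- Ratio: 0.55/0.12 = 4.6.
- Odds ratio: (0.55/0.45)/(0.12/0.88) = 9.0.

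Over the same assumed prevalences, kappa is about 0.34 to 0.45. The association is clear and the agreement moderate at best. The 55% is also not matched by drug: a report of any illicit drug counts as agreement, whichever drug was detected.

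**3. Could truthful reporting give 45%?** Assume that monthly use is independent with probability q and that the assay detects any use in 6 months. Then P(use in the last 30 days | any use in 6 months) = q/(1 − (1 − q)^6).

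- q = 0.2: 0.2/0.738 = 27%
- q = 0.3: 0.3/0.882 = 34%
- q = 0.4: 0.4/0.953 = 42%
- q = 0.5: 0.5/0.984 = 51%

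So 49% to 73% of nail-positive men could truthfully report no use in the last 30 days. With more persistent use, q = 0.7 gives 0.7/(1 − 0.3^6) = 70%. Truthful non-report is then 30%, which leaves 15 of the 45 points unexplained. The published figures fit either case.

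**4. Which nail samples are usable?** With a 6-month look-back and visits allowed 15 days early:

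- 3 months: reaches about 3 months before baseline.
- 6 months: reaches to baseline, or 15 days before it.
- 9 months: starts about 3 months after baseline, or 2.5 months if early. This is after baseline but can overlap the 12-week session period.
- 12 months: starts about 6 months after baseline, or 5.5 if early. This is clear of the sessions.

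**5. What could a nail comparison detect?** The documents give no nail-positive rate, so I assume 20% to 50% in Education, with two-sided alpha of 0.05, 80% power and a two-proportion normal approximation. The detectable difference is 12.5 to 17.8 points at 120 per arm. It is 13.7 to 19.8 points at 96 per arm (0.80 × 120, the 80% retention used under Power analyses).

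**The case against.** The strongest reply is that the disagreement has innocent causes. A man who used three months ago is correctly nail positive and correctly reports zero days in the last 30. For cannabis, the men who disagree with the assay are mostly admitting use, not hiding it. For illicit drugs, the contrast of 55% with 12% is real evidence that reports track the assay. Education is attention-matched and covers drug use in three of its four sessions, so pressure to report less is not confined to PARTNER. Details may also be in supplemental material that is not part of this document.

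Most of this stands, and it rules out several stronger readings that a reader might infer:

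- *That the claim fails altogether.* It does not for illicit drugs, once the 12% comparator is counted.
- *That 45% of users conceal use.* Step 3 shows that truthful reports could produce that share.
- *That the bias can be sized.* An assumed non-report split of 45% in PARTNER and 35% in Education would give an apparent ratio of 0.55/0.65 = 0.85 with no true effect. But that split is invented, no by-arm figures exist, and the nail-positive drugs are only part of the illicit outcome. No false-positive rate follows from the documents.
- *That the nail results go unused.* Equivalency Checks applies biological markers at baseline.

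The reply does not restore the word *corroborated*. Data that fit both truthful reporting and substantial under-reporting do not confirm the self-report. An assay that most often fails to flag cannabis in men who admit recent use says little about it either way.

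A nail-based check has limits too. A yes/no result over 6 months cannot verify a 30-day count, and it misses some drugs in the outcome. It can therefore support the day-count model but cannot replace it.

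**Conclusion.** The concern holds in a limited form. For cannabis, the statement of corroboration is not supported: the reporting ratio between nail-positive and other men is at most 1.67, and the difference in window does not account for it. For illicit drugs it is partly supported: 55% against 12%, with up to 45% of nail-positive men at the worst visit reporting none. The documents do not allow that 45% to be divided between the longer assay window and under-reporting, and they give no agreement by arm. The unblinded, one-sided self-report result therefore has less objective support than the text says. Nothing here shows that reporting differed by arm or that any observed benefit would be false.

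The percentages rest on the document as printed. The 1.67 limit assumes that the 60% applies at each visit and to men with a negative result. The kappa values, the window calculation and the detectable differences rest on the assumed prevalences and use rates stated with them. The 6-month look-back appears in the pre-COVID text, and I take it to apply to mailed kits as well.

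**What to change.** 1. Replace *corroborated* for drug use with a statement of partial agreement. Give counts and confidence intervals by arm and visit, show men without a usable nail sample separately, and state the difference in window (6 months against 30 days) and in drugs covered.
2. Add one supportive between-arm analysis of nail positivity alone for the assayed illicit drugs. Make 12 months the main time point; 9 months is also usable. Adjust for baseline nail status and the stratification variables. Do not combine nail result and self-report in one outcome: that would bring back the reporting difference being checked and mix two windows.
3. Report the estimate with its confidence interval beside the day-count model. Note that any use in 6 months cannot register fewer use days without abstinence, and that the comparison is sensitive only to fairly large differences.
4. Describe a drug-use benefit as self-reported only unless the nail result supports it. Judge support from the estimate and its interval. A rule based only on the direction of the estimate would often be triggered by chance.

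The cost is one extra model on samples already collected, plus revised wording. The stated support for self-report becomes less favourable.
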